#### **7.1 Sample Size Considerations**

This is a feasibility study. Results gathered here will inform future sample, effect, and power calculations.

#### **7.2 Planned Analyses**

This is an observational study that will evaluate the feasibility of implementing a brief training and assessment protocol to assess for undiagnosed cognitive impairment and dementia in ED patients and refer those at risk for outpatient evaluation. The ED assessment protocol, referral process, and outpatient evaluation will be integrated into clinical care. Researchers will gather observational data about these processes to measure the proportion of patients who are at risk in the emergency department, number of patients who are referred to the outpatient setting up to 3 months post-discharge and number of patients who evaluated who are diagnosed with cognitive impairment. These sample sizes will provide estimates needed for future larger scale pragmatic evaluation of such clinical care and its impact on patient and caregiver outcomes.

##### **7.2.1 Interim Analysis (if applicable)**

An interim analysis will be conducted at 2-months from the start of data collection. This will be done for the purposes of safety and efficacy monitoring.

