### **2.3 Anticipated Benefits**

The potential benefits to study participants include the opportunity for clinical assessments affirming or clearing risk of suspected dementia or related diseases, the coordination and communication about these results with your primary care provider, and receipt of brain health plans if deemed necessary. The benefit to society is the generation of knowledge to improve the care and outcomes of older persons presenting to the ED. As an observational study with no therapeutic intent, the only alternative is for patients to choose not to participate. Therefore, all patients will receive standard clinical care as determined by their physician irrespective of study participation.

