#### 4 Study Design

This is a multicenter, single-protocol observational pilot pragmatic intervention study that consists of both retrospective and prospective data collection.

The pragmatic intervention that will be evaluated consists of 3-steps: 1. ED assessment for cognitive impairment and outpatient referral, 2. Outpatient assessment and evaluation, and 3. Cognitive Brain Health Planning. For a schematic of the pragmatic intervention, see Figure 1.

Figure 1. Proposed PD4ED Intervention Structure:

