#### **5.2 Number of Participants**

All patients 65+ years in age seen in both EDs during the study period will be screened in the ED using clinical screening for UCID.

A convenience sample of 100 hundred subjects (50 from each site) will be included for retrospective and prospective observational data via chart review and interview to evaluate rate of UCID detection in the ED, rates of referral for outpatient evaluation, rates of confirmed cognitive impairment or dementia by the outpatient evaluation, and differences across the two sites with processes, utilization, and outcome endpoints.

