## **6 Study Methods/Procedures**

### **6.1 Study Procedures**

#### **Clinical ED Practice Intervention.**

As part of routine ED care, clinicians conduct delirium screening at bedside to evaluate presence of cognitive impairment in ED who are 65 years and older. The intervention will augment this process to include questions assessing for documented history of dementia or asking the patient, or caregivers present, in the ED if the patient has had any memory or thinking problems in the past year. If clinicians suspect the patient may have cognitive impairment, regardless of the response from patient or caregiver, and the patient has no documented history of dementia, the physicians may refer these patients to available outpatient cognitive evaluation. Referral will occur using EMR outpatient consult requests or by emailing outpatient clinics for available appointments as part of routine patient care referral processes.

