### **7 Statistical Design**

This is an observational pilot study and descriptive statistics will be completed comparing demographic and clinical characteristics of all patients 65+ discharged from the ED (denominator) versus those referred from the ED for outpatient cognitive impairment assessment. Student's t-test will be used for continuous variables (if normally distributed (e.g. age)) or the Wilcoxon rank-sum test (if not normally distributed (e.g., length of stay)), and the Chi-square test or Fisher's exact test for binary/categorical variables. All tests will be 2-sided at a significance level of 5%.

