#### **7.3 Data Relevance**

Data analyses will consist of descriptive statistics comparing overall eligible subjects at both sites and of the subset of 100 patients for which chart review will be completed.

A valid analysis of the intervention effect between gender and racial/ethnic subgroups will be completed to identify differences between the subgroups and their characteristics.

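### Sections 7.2.1 and 7.3 promise efficacy monitoring and a subgroup intervention effect, but no planned comparison has a group or period without the intervention, so the study can give rates and rate differences only.

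*Combined protocol and SAP*

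**What the plan says.** Section 7.2.1 commits to one interim analysis "at 2-months from the start of data collection. This will be done for the purposes of safety and efficacy monitoring". Section 7.3 adds: "A valid analysis of the intervention effect between gender and racial/ethnic subgroups will be completed to identify differences between the subgroups and their characteristics".

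On design, section 4 says: "This is a multicenter, single-protocol observational pilot pragmatic intervention study". Section 2.3 begins its account of alternatives to participation with "As an observational study with no therapeutic intent". Section 6.2 marks assignment and randomization as not applicable. Section 5.2 says that all patients aged 65 or over "seen in both EDs during the study period will be screened in the ED using clinical screening for UCID". Section 4.2 states that no hypotheses are tested and that the results will inform effect sizes for a later full-scale study.

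**The concern.** Efficacy and intervention effect are comparative quantities: what happened with the intervention, less what would have happened without it. A plan that promises them needs some source for the second term, such as an unexposed group, a pre-launch period or a justified external rate. If there is none, an observed rate or a subgroup gap may be reported as something the intervention caused when part of it reflects earlier practice. Because 4.2 and 7.1 feed the results into effect-size and power calculations for the next trial, a mislabelled rate could be carried into that planning. The risk lies in what is concluded and passed on, not in the conduct of this study.

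**Working it through.** The plan states no figure to reproduce here: it gives no expected rates, effect size or precision target. The main check is therefore of the text.

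**Step 1. Does any planned comparison have an unexposed side?**

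| Comparison | Where | Group or period without the intervention? |
|---|---|---|
| Demographic and clinical characteristics "of all patients 65+ discharged from the ED (denominator) versus those referred from the ED for outpatient cognitive impairment assessment" | 7 | No; both come from EDs running the intervention |
| All eligible patients and the 100 charted subjects | 7.3 | No |
| All ED records in the age group and the enrolled subjects | 5.5 | No; same study period |
| Site against site | Synopsis (Number of Participants), 5.2 | No; both sites run it |

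The two-sided 5% tests in section 7 belong to the first row. They compare characteristics, so they do not supply an effect.

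**Step 2. Do the data contain a comparator that the plan does not use?** There are two candidates.

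- Section 6.1.1 abstracts utilization up to 6 months before the ED visit. No before-after analysis of it is planned, and utilization is not the screening outcome.
- Some patients may go unscreened or unreferred: 6.1.1 reviews clinician compliance, and 6.1 leaves referral to the physician. No outcome comparison with them is planned, and clinicians' choice of whom to screen or refer would confound one.

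**Step 3. What separates a rate from an effect?** For subgroup g, let r_g be the rate observed in the study and b_g the rate that would have been seen without the intervention. Then

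- effect in subgroup g = r_g − b_g
- difference in effect between A and B = (r_A − r_B) − (b_A − b_B)

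The study measures r_A and r_B but neither b. The subgroup rate difference equals the difference in effect only if b_A = b_B, and an overall rate equals an effect only if b = 0.

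**Step 4. What do the documents say about b?**

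- Delirium screening: b is above zero. Section 6.1 states: "As part of routine ED care, clinicians conduct delirium screening at bedside to evaluate presence of cognitive impairment". The intervention augments this.
- Memory and dementia questions: unknown. Section 1.1 says that dementia assessment is not traditionally done in the ED, and 3.1 calls the protocol new. Both point to a low b.
- Referral: 6.1 says that requests go by EMR consult or by email to clinics "for available appointments as part of routine patient care referral processes". This describes the route. It does not show how often cognitive referrals were made before.

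**Step 5. How precise would subgroup rate differences be?** The 95% half-width is 1.96 × √[p(1−p)(1/n₁ + 1/n₂)]. The 100 is from 5.2. The splits, rates p and EMR cohort sizes are assumptions, because the documents give none.

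| N | 50/50 split, p = 0.2 | 80/20 split, p = 0.5 |
|---|---|---|
| 100 | 1.96 × √(0.16 × 0.04) = 15.7 points | 1.96 × √(0.25 × 0.0625) = 24.5 points |
| 2,000 | 1.96 × √(0.16 × 0.002) = 3.5 points | 1.96 × √(0.25 × 0.003125) = 5.5 points |
| 10,000 | 1.96 × √(0.16 × 0.0004) = 1.6 points | 1.96 × √(0.25 × 0.000625) = 2.45 points |

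This concerns precision, not the missing comparator. It shows where subgroup rate differences are worth estimating.

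**The case against.** The strongest reply is that this is loose wording in a descriptive study. Sections 7, 7.2 and the first sentence of 7.3 speak of descriptive statistics, proportions and counts, and 4.2 disclaims hypothesis tests. The subgroup sentence gives its own aim, to identify differences between subgroups, and rate differences meet that aim. Efficacy at the interim could mean screening or referral performance against a target, which needs no comparator. Section 8.6, the Data and Safety Monitoring Plan in the table of contents, was not available for review and may hold such a single-group criterion. No section says that the interim or subgroup result is the effect size to be carried forward.

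Much of this stands, and it is why a rewording largely settles the point. It does not rescue the text as written: a single-group criterion would define performance against a target, and would still not yield an intervention effect by gender or race/ethnicity.

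A reader might also infer that prior practice contaminates every rate heavily. The documents support this for delirium screening only. If the prior rate for the dementia questions lay between 0 and 5% in both subgroups (an assumption), b_A − b_B would lie between −5 and +5 points, and the rate difference would be within 5 points of the difference in effect.

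**Conclusion.** The point holds and should be fixed. Nothing planned in the available text can estimate efficacy or a subgroup intervention effect. Screening, detection and referral rates, and their differences between subgroups and sites, can be estimated, and the safety part of the interim is unaffected. The gap between rate and effect cannot be sized from the documents, since no pre-launch rate is given or collected for screening or referral. The delirium screening rate in particular cannot be read as an effect.

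Three stronger readings are not supported:

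- That every patient is exposed. Section 5.2 states the intent to screen everyone, but some may go unscreened or unreferred.
- That the interim inflates type I error or lacks stopping rules. The available text attaches no test or stopping decision to the look, and 8.6 could not be checked.
- That the look falls only after follow-up has ended, because 4.1 lists data collection after enrolment and follow-up. The schedule in 6.1.1 collects data from Day 0, so that reading is strained. The start of data collection has no date of its own, however, and the fix should anchor it.

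The enrolment-period mismatch between 4.1 and 9.6 is a separate, minor matter.

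**What to change.** (a) In 7.2.1, write: *Two months after the first study ED visit, safety and feasibility (numbers screened, detected, referred, consented and contacted, and adverse events) will be summarised descriptively by site. No efficacy conclusion will be drawn.*

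(b) In 7.3, replace the intervention effect with: *between-subgroup differences in rates, with 95% confidence intervals, by gender and race/ethnicity, from EMR records: screening and detection in all ED patients aged 65 or over, and referral in discharged patients who meet 5.3. Subgroup results in the 100 interviewed subjects are descriptive only.*

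The cost is low. The 2-month look stays, and the EMR records are already sought under 5.5. The price is a little more analysis, the loss of any efficacy claim, and possibly a phrase added to the waiver purpose in 5.5, which now covers those records for comparison with the enrolled population. Keeping either comparative term would instead require a defined pre-launch or unexposed comparator, which is a design change that this fix does not ask for.

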#### **7.3 Data Relevance**

Data analyses will consist of descriptive statistics comparing overall eligible subjects at both sites and of the subset of 100 patients for which chart review will be completed.

A valid analysis of the intervention effect between gender and racial/ethnic subgroups will be completed to identify differences between the subgroups and their characteristics.

#### **7.4 Data Coding**

Data will be coded by unique study ID for each participant.

#### **7.5 Data Analysis Tools**

Software use to analyze the data will include SAS, SPSS, and Stata.

## **7.6 Data Monitoring**

See Data Safety Monitoring Board in Section 8 Below

## **7.7 Handling of Missing Data**

As this is an observational study to guide future study design, missing data will be informative in this study. Missing data will be used to identify unexpected problems likely to occur in a future study.

# **8 Data/Specimen Handling and Record Keeping**

## **8.1 Subject Data Confidentiality**

Participant confidentiality and privacy is strictly held in confidence by the participating investigators, their staff, and the sponsor(s)/funding agency. Therefore, the study protocol, documentation, data, and all other information generated will be held in strict confidence.

All research activities will be conducted in as private a setting as possible.

Representatives of the Institutional Review Board (IRB), regulatory agencies or study sponsor/funding agency may inspect all documents and records required to be maintained by the investigator for the participants in this study. The study site will permit access to such records.

The study participant's contact information and data will be securely stored at each study site for internal use during the study. At the end of the study, all records will continue to be kept in a secure location for as long a period as dictated by the reviewing IRB, Institutional policies, regulatory, or sponsor/funding agency requirements.

## **8.2 Data Quality Assurance**

All research staff will be required to complete institutional research ethics and compliance training. This will occur online. Research staff will also be required to complete all institutional trainings. The PI and project manager will conduct an in-person training for the research staff that will include key topics essential to conducting clinical research in the emergency department. The training will also include a thorough review of the EMR chart review processes, and the requirement of replicating five gold standard abstractions of identified patients.

## **8.3 Data or Specimen Storage/Security**

The data be collected by the research assistant and stored on the hospital's encrypted secured servers. Participants will be assigned unique participant identification codes. Only assigned custodians who are part of the protocol will have access to the logs and passwords. The log will also include a tracker to document patients who participate in the outpatient assessments. Assigned custodians will have to be on hospital grounds or must connect using Virtual Private Network (VPN) with two-factor authentication to access the hospital servers.

## **8.4 Access to Source**

For identification of eligible participants for recruitment and enrollment, research staff will maintain a password protected screening log to track patients who are referred from the ED

for outpatient cognitive assessment. Participants enrolled will be assigned generated participant identification codes to facilitate the de-identification process.

Data will be collected and merged from clinical and administrative reports and chart review by trained research staff into a single Redcap database.

As this use of administrative and retrospective clinical data and chart review are only minimal risk a waiver of signed consent will be requested.

Source data are all information, original records of clinical findings, observations, or other necessary activities in a research study. Source data are contained in source documents. Research staff at the local site will access the following source documents to extract data for medical record abstraction including: ED records, inpatient records, readmission records, consultations, outpatient records (clinical and office charts), medication administration records and other reports.

## **8.5 Retention of Records**

In compliance with NIH guidance, it is the PI's responsibility to retain study essential documents for 3 years from the date of submission of Yale's federal financial report (FFR) to NIH.

## **9 Study Considerations**

### **9.1 Institutional Review Board (IRB) Review**

The study will use Advarra as the IRB of record as required by the sponsor.

### **9.2 Research Personnel Training**

All research staff will be required to complete research ethics and compliance training as prescribed by their home institution. The PI and project manager will conduct an in-person training for the research coordinator that will include key topics essential to conducting clinical research in the emergency department. The training will also include a thorough review of the EMR chart review processes, and the requirement of replicating five gold standard abstractions of identified patients

### **9.3 Study Monitoring**

The PI will review monthly the data quality collected by the research assistant, and administrative and clinical data reports generated of aggregate monthly ED patient metrics. A Safety Officer and Data Safety Monitoring Board will review this study quarterly with online meetings reviewing study progress. Since this is an observational study with minimal risk, we do not anticipate any risk of severe adverse events occurring in association with the study.

### **9.4 Unanticipated Problems and Protocol Deviations**

This protocol will be conducted in accordance with Good Clinical Practice of the International Council of Harmonization (ICH GCP) and will safeguard the rights and well-being of the study participants. A protocol deviation will be defined as divergence from the procedures outline in the protocol. An unanticipated problem may include events like subject or caregiver complaints related to safety, welfare, or rights of the patient or caregivers. The PI and project manager will review cases on a weekly basis and utilize a decision tree to guide the identification of protocol deviations. If the PI and project manager determine a protocol deviation has occurred, they will proceed to classify deviation and determine if it could impact the patients' well-being or the reliability of the study data. Deviations will be reported to the IRB for review and they will be documented in a deviation summary log.

### **9.5 Study Discontinuation**

Patients may discontinue clinical care at any time. Withdrawal will not impact delivery of their remaining medical care. The clinicians may discontinue patient care if adverse events are observed. Patients who discontinue care will not be replaced.

### **9.6 Study Completion**

We expect this study to complete recruiting by 12/31/21. Calendar year 2022 will be used for analysis, manuscript development, publications and closeout reports.

### **9.7 Conflict of Interest Management Plan**

The independence of this study from any actual or perceived influence is critical. Therefore, any actual conflict of interest of persons who have a role in the design, conduct, analysis, publication, or any aspect of this trial will be disclosed and managed. Furthermore, persons who have a perceived conflict of interest will be required to have such conflicts managed in a way that is appropriate to their participation in the trial. The study leadership in conjunction with the appropriate conflict of interest review committee has established policies and

procedures for all study group members to disclose all conflicts of interest and will establish a mechanism for the management of all reported dualities of interest.

All investigators will follow the applicable conflict of interest policies.

### **9.8 Funding Source**

National Institute of Aging through the IMPACT Collaborative

### **9.9 Publication Plan**

Publication of the results of this trial will be governed by the policies and procedures developed by the IMPACT Collaboratory. Any presentation, abstract, or manuscript will be made available for review by the sponsor and the NIA prior to submission.

